**Table 3 Routine Laboratory Parameters**

Clinical Chemistry	Hematology	Urinalysis

 
• Albumin
 
• ALT
 
• Alkaline phosphatase
 
• AST
 
• Bilirubin – total and direct
 
• Calcium
 
• Chloride
 
• Creatinine
 
• Creatine kinase
 
• Gamma-glutamyl transferase
 
• Potassium
 
• Sodium
 
	
 
• Hematocrit
 
• Hemoglobin
 
• Platelet count
 
• Red blood cell count
 
• White blood cell count
 
	
 
• Blood
 
• Glucose
 
• Ketones
 
• Leukocytes
 
• Nitrites
 
• pH
 
• Protein
 

## 10.2.2 Individual Patient Safety Monitoring

### 10.2.2.1 Liver Monitoring

Strategies to monitor markers of liver disease throughout the study are outlined below where the ULN will be based on central laboratory reference values for age and gender.

#### If isolated transaminase elevations are observed, defined as:

1. Normal bilirubin AND absence of clinical hepatitis symptoms AND

- ALT or AST  $\geq 5 \times$  ULN (if normal at baseline) or an absolute threshold of 800 U/L, whichever comes first
- OR ALT or AST  $\geq 3 \times$  baseline (if abnormal at baseline) or an absolute threshold of 800 U/L, whichever comes first

Then:

- a) Repeat liver profile (AST, ALT, bilirubin, and prothrombin time [PT] or INR) within 2 to 3 days
- b) Evaluate creatine phosphokinase (CPK) and lactate dehydrogenase (LDH)
- c) As needed (for example, persistent ALT/total bilirubin elevation or worsening of liver function), consider evaluation for alternative etiologies

Monitor the patient using close observation found in [Section 10.2.2.2](#)

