**If any ONE of the following criteria are met:**

1. Transaminases (ALT or AST  $\geq 3 \times$  baseline or 800 U/L, whichever comes first) AND bilirubin (total bilirubin  $> 2 \times$  ULN) elevations
2. Transaminase elevations alone (ALT or AST  $> 10 \times$  ULN or  $5 \times$  baseline or absolute threshold of 800 U/L, whichever comes first) in presence of normal LDH and CPK
3. Cholestatic marker elevations (alkaline phosphatase [ALP] or gamma-glutamyl transferase  $> 2 \times$  baseline) without alternative explanation
4. Total bilirubin increased, unrelated to hemolysis (elevated reticulocyte count) or established genetic diseases, such as Gilbert's syndrome
  - a. Doubling if total bilirubin was  $< 3$  mg/dL at baseline
  - b. OR Increase by  $> 3$  mg/dL if total bilirubin was  $\geq 3$  mg/dL at baseline
5. INR increase refractory to vitamin K administration
  - a. Increase by  $> 1.5$  if INR was normal at baseline
  - b. OR Increase by  $> 0.4$  if INR was abnormal at baseline
6. Any increase in total bilirubin and transaminases if accompanied by EITHER a symptom of clinical hepatitis (e.g., vomiting, nausea, right upper quadrant pain) OR immunological reaction (rash or  $> 5\%$  eosinophilia)

Then:

- a) Interrupt study medication
- b) Initiate drug-induced liver injury work-up for alternative etiologies
- c) Repeat liver profile (AST, ALT, total bilirubin, direct bilirubin, ALP) and PT or INR within 48 to 72 hours

- d) Monitor the patient using close observation found in [Section 10.2.2.2](#)
- e) If a patient lives in a remote area, they may be tested locally and the results communicated to the investigator site promptly

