#### **10.2.2.2 Close Observation**

- Repeat liver enzyme and serum bilirubin tests two or three times weekly. Frequency of re-testing can decrease to once a week or less if abnormalities stabilize or the trial drug has been discontinued and the subject is asymptomatic
- Obtain a more detailed history of symptoms and prior or concurrent diseases
- Obtain a history of concomitant drug use (including non-prescription medications and herbal and dietary supplement preparations), alcohol use, recreational drug use, and special diets
- Rule out alternate etiology including acute viral hepatitis types A, B, C, D, and E; autoimmune or alcoholic hepatitis; non-alcoholic steatohepatitis; hypoxic/ischemic hepatopathy; and biliary tract disease
- Obtain a history of exposure to environmental chemical agents.
- Obtain additional tests to evaluate liver function, as appropriate (e.g., INR, direct bilirubin)
- Consider gastroenterology or hepatology consultations.

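### An asymptomatic ALT/AST rise to 3 x an abnormal baseline has no written action when bilirubin is between 1 and 2 x ULN, although it gets close observation below that band and interruption above it

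*Protocol*

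**What the plan says.** Section 10.2.2.1 (Liver Monitoring) has two tiers, with ULN taken from central laboratory ranges for age and gender.

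- **Close-observation tier (isolated transaminase elevations).** Entry requires "Normal bilirubin AND absence of clinical hepatitis symptoms AND" one of these: ALT or AST at least 5 x ULN if normal at baseline, at least 3 x baseline if abnormal at baseline, or 800 U/L. The actions are a repeat liver profile in 2 to 3 days, the step "Evaluate creatine phosphokinase (CPK) and lactate dehydrogenase (LDH"), and close observation under Section 10.2.2.2: "Repeat liver enzyme and serum bilirubin tests two or three times weekly".
- **Interruption tier (any one of six criteria).** Criterion 1 is ALT or AST at least 3 x baseline or 800 U/L "AND bilirubin (total bilirubin" above 2 x ULN). Criterion 2 is ALT or AST above 10 x ULN, 5 x baseline or 800 U/L, "whichever comes first) in presence of normal LDH and CPK". Criterion 3 concerns ALP or GGT above 2 x baseline. Criterion 4a begins "Doubling if total bilirubin was" below 3 mg/dL at baseline. Criterion 5 concerns INR. Criterion 6 reads "Any increase in total bilirubin and transaminases if accompanied by EITHER a symptom of clinical hepatitis" or an immunological reaction. Interruption includes close observation.

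Table 3 lists "Creatine kinase" as routine chemistry but not LDH. Section 7.2.2, criterion 14, excludes only total bilirubin above 5 x ULN.

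Every copy of Section 10.2.2.1 in the file has this wording. The text dated 20 September 2017 uses different rules under Section 10.2.2.

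**The concern.** A stopping algorithm should not become weaker as the patient's liver tests get worse. Here, at a fixed ALT, the written response goes from close observation, to nothing, to interruption as bilirubin moves from normal, through 1 to 2 x ULN, to above 2 x ULN. A child whose ALT and bilirubin rise together can get a weaker written response than one whose ALT alone rises.

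The band is a plausible place for these patients to be. The trial enrols children with cholestatic disease and bilirubin up to 5 x ULN, and Section 5.2.1 describes hyperbilirubinemia and raised ALT/AST as features of PFIC. A child whose bilirubin stays above ULN can never enter a tier that requires normal bilirubin.

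What is at stake is the safety monitoring of individual children. The primary efficacy analysis is not affected.

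**Working it through.** No figure in the plan needs reproducing; the check is whether the two tiers meet. The inputs are the thresholds above. Assumptions: ALT ULN of 30, 40 or 50 U/L; no symptoms, rash or eosinophilia; ALP, GGT and INR stable, so criteria 3, 5 and 6 are not met.

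**Step 1. ALT/AST range of the gap, LDH and CPK normal.** Let baseline be b x ULN with b > 1 and bilirubin between 1 and 2 x ULN. The lower tier is closed because bilirubin is not normal, and criterion 1 is closed because bilirubin is not above 2 x ULN. Criterion 2 starts at the lower of 5b and 10 x ULN. (The 800 U/L limit does not bind, since 10 x 50 = 500.) The gap therefore runs from 3b to min(5b, 10).

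| b | gap, x ULN |
|---|---|
| 1.5 | 4.5 to 7.5 |
| 2 | 6 to 10 |
| 3 | 9 to 10 |
| above 10/3 = 3.33 | none |

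In U/L, the baselines concerned are 30-100, 40-133 or 50-167 for the three ULNs. A normal baseline gives no gap here, because 5 x ULN is at least 5 x baseline and criterion 2 is already met.

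**Step 2. Bilirubin range of the gap.** Criterion 4a interrupts on doubling, so the open part of the band depends on baseline bilirubin (bilirubin ULN taken as 1.0 mg/dL).

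| baseline bilirubin, x ULN | open part of band, x ULN |
|---|---|
| 0.5 | none |
| 0.6 | 1.01 to 1.19 |
| 0.8 | 1.01 to 1.59 |
| 1.0 | 1.01 to 1.99 |
| 1.2 or more | 1.01 to 2.0 |

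A rise from 0.9 to 1.7 x ULN is a factor of 1.7/0.9 = 1.89. It is not a doubling, so that patient stays in the gap.

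**Step 3. Worked case.** ALT goes from 80 to 280 U/L, which is 280/80 = 3.5 x baseline and from 280/50 = 5.6 to 280/30 = 9.3 x ULN. With bilirubin not doubled, the result is the same at all three ULNs:

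| bilirubin | written action |
|---|---|
| normal | close observation |
| 1.5 x ULN | none |
| 2.5 x ULN | interruption |

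**Step 4. LDH or CPK raised.** ALT goes from 100 to 600 U/L, 6 x baseline, so criterion 2's limit is reached at any of the ULNs. With LDH and CPK normal, the drug is interrupted at every bilirubin level. With LDH raised, the response is close observation at normal bilirubin, nothing at 1.5 x ULN, and interruption at 2.5 x ULN. LDH is explicitly ordered only in the normal-bilirubin tier, which this patient cannot enter.

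**Step 5. Default follow-up.** Table 1 schedules chemistry on Days 28, 56, 84, 126 and 168, and not at Visit 8 (Day 154). The waits after Days 28, 56, 84 and 126 are 28, 28, 42 and 42 days.

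**Step 6. Test of the repair.** I enumerated 821,340 combinations (three ULNs; baseline 10-398 U/L; ALT 20-795 U/L; nine bilirubin levels from 0.5 to 5 x ULN, held stable). Combinations at a lower-tier ALT threshold with no action:

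| | current text | bilirubin limit set to 2 x ULN |
|---|---|---|
| LDH and CPK normal | 11,328 | 0 |
| LDH raised | 113,876 | 0 |

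These counts show only that the gap closes. They are not patient shares.

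**The case against.** The strongest reply is that the gap needs many conditions at once: baseline ALT between 1 and 3.33 x ULN, a rise of 3 to under 5 x, both transaminases under criterion 2's limits, bilirubin in a narrow band and not doubled, and nothing else moving. Much of the band will be children with chronic, stable bilirubin of 1 to 2 x ULN, where nothing has newly risen. That limits the frequency, which is unknown. It does not supply an action for the patients who are there.

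Second, oversight exists outside these rules. Investigators assess every untoward event (Section 10.1.2). Extra visits (7.1.1), extra samples (10.2.1) and withdrawal (7.2.3) are allowed, and the DSMB periodically reviews liver values (11.2.4). All true, but none sets a threshold, timing or action for this patient.

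Third, criterion 2 implies that LDH and CPK will be measured, and its qualifier evidently exists to avoid automatic interruption when they are raised. That is fair. It explains not interrupting; it does not explain dropping the close observation that the same result gets at normal bilirubin.

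Fourth, the repaired tier could overlap with criterion 4a: bilirubin from 0.9 to 1.9 x ULN is a factor of 2.11 and would meet both. This is harmless. The present tier already overlaps with criteria 2 and 4a, and interruption includes close observation.

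Finally, the file is marked as part 3 of 3, so a later version might differ. Nothing in the document shows that it does.

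**Conclusion.** The concern holds and should be fixed. Read as written, Section 10.2.2.1 gives no action for an asymptomatic ALT/AST of 3b up to the lower of 5b and 10 x ULN, for baselines b from just above 1 to 3.33 x ULN, when bilirubin is between 1 and 2 x ULN and has not doubled. If LDH or CPK is raised, the gap extends to the values criterion 2 would otherwise catch, and to baselines outside that range.

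The bounds in multiples of ULN do not depend on the assumed ALT ULN, provided 10 x ULN stays below 800 U/L; the U/L examples use 30 to 50. The conclusion also assumes that criteria 3, 5 and 6 are not met. If the word *alone* in criterion 2 is taken to mean without raised bilirubin, criterion 2 would not apply in the band at all and the gap would be wider. The number of children affected cannot be estimated from the document.

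**What to change.** In the isolated-elevation tier of Section 10.2.2.1, replace the normal-bilirubin condition with total bilirubin at or below 2 x ULN, so that the tier meets criterion 1 without a gap. State that LDH and CPK are measured whenever an ALT/AST threshold in that tier or in criterion 2 is reached. It would help to add that interruption takes precedence where both tiers apply.

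The cost is a wording amendment and an LDH assay on samples that are being repeated anyway. Children with mildly raised bilirubin who reach these thresholds would also have the extra draws and the search for other causes that Section 10.2.2.2 requires. That burden is real in small children, but retesting can be reduced once values stabilise.

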**If any ONE of the following criteria are met:**

1. Transaminases (ALT or AST  $\geq 3 \times$  baseline or 800 U/L, whichever comes first) AND bilirubin (total bilirubin  $> 2 \times$  ULN) elevations
2. Transaminase elevations alone (ALT or AST  $> 10 \times$  ULN or  $5 \times$  baseline or absolute threshold of 800 U/L, whichever comes first) in presence of normal LDH and CPK
3. Cholestatic marker elevations (alkaline phosphatase [ALP] or gamma-glutamyl transferase  $> 2 \times$  baseline) without alternative explanation
4. Total bilirubin increased, unrelated to hemolysis (elevated reticulocyte count) or established genetic diseases, such as Gilbert's syndrome
  - a. Doubling if total bilirubin was  $< 3$  mg/dL at baseline
  - b. OR Increase by  $> 3$  mg/dL if total bilirubin was  $\geq 3$  mg/dL at baseline
5. INR increase refractory to vitamin K administration
  - a. Increase by  $> 1.5$  if INR was normal at baseline
  - b. OR Increase by  $> 0.4$  if INR was abnormal at baseline
6. Any increase in total bilirubin and transaminases if accompanied by EITHER a symptom of clinical hepatitis (e.g., vomiting, nausea, right upper quadrant pain) OR immunological reaction (rash or  $> 5\%$  eosinophilia)

Then:

- a) Interrupt study medication
- b) Initiate drug-induced liver injury work-up for alternative etiologies
- c) Repeat liver profile (AST, ALT, total bilirubin, direct bilirubin, ALP) and PT or INR within 48 to 72 hours

- d) Monitor the patient using close observation found in [Section 10.2.2.2](#)
- e) If a patient lives in a remote area, they may be tested locally and the results communicated to the investigator site promptly

#### **10.2.2.2 Close Observation**

- Repeat liver enzyme and serum bilirubin tests two or three times weekly. Frequency of re-testing can decrease to once a week or less if abnormalities stabilize or the trial drug has been discontinued and the subject is asymptomatic
- Obtain a more detailed history of symptoms and prior or concurrent diseases
- Obtain a history of concomitant drug use (including non-prescription medications and herbal and dietary supplement preparations), alcohol use, recreational drug use, and special diets
- Rule out alternate etiology including acute viral hepatitis types A, B, C, D, and E; autoimmune or alcoholic hepatitis; non-alcoholic steatohepatitis; hypoxic/ischemic hepatopathy; and biliary tract disease
- Obtain a history of exposure to environmental chemical agents.
- Obtain additional tests to evaluate liver function, as appropriate (e.g., INR, direct bilirubin)
- Consider gastroenterology or hepatology consultations.

#### **10.2.2.3 De-challenge/Re-challenge for Liver and Clinical Hepatitis Monitoring**

1. Re-challenge is not recommended:
  - a. If a patient has had possible/probable drug-induced liver injury
  - b. If a decompensation event has occurred (i.e., variceal hemorrhage, ascites, hepatic encephalopathy, etc.).
2. If due to underlying cholestatic liver disease variability or another alternative etiology is identified AND liver tests returned to baseline, re-challenge may be considered after consultation with the sponsor Medical Monitor.
3. If the ALT/total bilirubin elevations are observed after re-challenge, then repeat re-challenge is discouraged.

If patient is permanently discontinued, monitoring should be continued as outlined in [Section 10.2.2.5](#).

#### **10.2.2.4 Diarrhea**

Study drug should be discontinued if a patient develops diarrhea with at least 1 of the following concomitant signs or symptoms: grossly bloody stools, vomiting, dehydration

requiring treatment with oral or intravenous rehydration and/or electrolyte imbalances, fever ( $\geq 38$  C) and/or the diarrhea persists for 7 or more days.

If there is gross blood in stool, INR and platelets should be measured.

Study drug will be reintroduced (re-challenge) when the symptoms have resolved. If the diarrhea re-occurs within 1 week after the re-challenge with no alternate etiology, the patient will be permanently discontinued and monitored as outlined in [Section 10.2.2.5](#).

#### **10.2.2.5 Monitoring after Permanent Discontinuation of Study Drug Due to Safety**

Once study drug is permanently discontinued for liver, hepatitis, diarrhea, or other severe AE related to study drug, the patient will be monitored weekly until the laboratory and clinical parameters have normalized/stabilized.

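### After a permanent stop for a liver reason, a child who is still symptomatic with unstable tests falls under two different testing frequencies: two or three times weekly (Section 10.2.2.2) and weekly (Section 10.2.2.5)

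*Protocol*

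**What the plan says.** Four parts of Protocol Section 10.2.2 bear on this.

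- **Section 10.2.2.1, interruption criteria.** Six criteria lead to interruption of study drug. The sixth is any rise in total bilirubin and transaminases "if accompanied by EITHER a symptom of clinical hepatitis" or an immunological reaction. For all six, the liver profile is repeated, "and PT or INR within 48 to 72 hours", and the site is told "Monitor the patient using close observation found in" Section 10.2.2.2.
- **Section 10.2.2.2, Close Observation.** The standing rule is "Repeat liver enzyme and serum bilirubin tests two or three times weekly". The frequency "can decrease to once a week or less if abnormalities stabilize or the trial drug has been discontinued and the subject is asymptomatic".
- **Section 10.2.2.3, De-challenge/Re-challenge.** Re-challenge is not recommended "If a patient has had possible/probable drug-induced liver injury" or after a decompensation event. The section ends with a hand-off: "If patient is permanently discontinued, monitoring should be continued as outlined in" Section 10.2.2.5.
- **Section 10.2.2.5, after permanent discontinuation for safety.** For liver, hepatitis, diarrhea or another severe related event, "the patient will be monitored weekly until the laboratory and clinical parameters have normalized/stabilized".

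The protocol file contains several printings of the text. The wording of Sections 10.2.2.2, 10.2.2.3 and 10.2.2.5 is the same in all three printings that contain them. The printing dated 20 September 2017 has a different liver monitoring section and is not at issue.

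**The concern.** Close observation makes less frequent testing depend on the patient's condition: either the abnormalities have settled, or the drug is off and the patient has no symptoms. Section 10.2.2.5 makes it depend only on the stop being permanent. It runs until findings have normalized or stabilized, so by its own terms it covers patients whose tests are still moving, and it says nothing about symptoms.

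What is at stake is patient safety and uniform conduct across sites. A site that follows the hand-off in Section 10.2.2.3 literally can cut testing in a symptomatic child with changing liver tests at the moment the stop is declared permanent. A site that reads weekly as a minimum would carry on two or three times weekly. The patients concerned are foreseeable, because suspected drug-induced liver injury and decompensation are the cases in which re-challenge is not recommended. No efficacy endpoint, error rate or power figure depends on this.

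**Working it through.** The protocol states no figure to reproduce. The check is to apply both rules to the same patient, then count tests.

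**Step 1. Two readings of the step-down sentence in Section 10.2.2.2.** Its mix of *or* and *and* can be parsed in two ways:

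- Reading A: stable, or (off drug and asymptomatic).
- Reading B: (stable or off drug), and asymptomatic.

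**Step 2. Patients permanently off drug for a liver or hepatitis reason, tests not yet stable.**

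| Patient state | 10.2.2.2, reading A | 10.2.2.2, reading B | 10.2.2.5 | Do they agree? |
|---|---|---|---|---|
| Asymptomatic | weekly or less allowed | weekly or less allowed | weekly | yes |
| Symptomatic | 2 to 3 per week | 2 to 3 per week | weekly | no |

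The disagreement in the second row does not depend on how the sentence is parsed. Once the tests have stabilized, the ordinary reading (A) permits weekly testing and there is no conflict.

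**Step 3. Does the hand-off resolve it?** Section 10.2.2.2 itself mentions the patient whose drug has been discontinued and still requires that patient to be asymptomatic unless the abnormalities have stabilized. Neither Section 10.2.2.3 nor Section 10.2.2.5 says that close observation ends or that this condition is waived. Section 10.2.2.5 also does not say that weekly is a minimum.

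**Step 4. Size while the patient is both symptomatic and unstable.**

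- Tests per week: 1 (Section 10.2.2.5) against 2 to 3 (Section 10.2.2.2), a ratio of 2 to 3.
- Average spacing: 7/1 = 7 days against 7/2 = 3.5 days and 7/3 = 2.3 days. For comparison, Section 10.2.2.1 wants the first repeat within 48 to 72 hours, which is 2 to 3 days.
- Extra tests per week under Section 10.2.2.2: 2 − 1 = 1 to 3 − 1 = 2.

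The protocol does not say how long this state lasts. The durations below are assumptions:

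| Assumed duration | Tests, 10.2.2.5 | Tests, 10.2.2.2 |
|---|---|---|
| 1 week | 1 | 2 to 3 |
| 2 weeks | 2 | 4 to 6 |
| 4 weeks | 4 | 8 to 12 |

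**The case against.** The strongest reply is that the protocol puts the sections in sequence. Interruption leads to close observation, and permanent discontinuation leads to Section 10.2.2.5, whose title names that state, so the later and more specific rule governs. In support, Section 10.2.2.4 uses the word discontinued for a stop that is followed by re-challenge, so its use in Section 10.2.2.2 need not mean a permanent stop. This is a fair reading, but it does not remove the problem. It means that a symptomatic child with unstable tests is tested two or three times weekly while the stop is temporary and once weekly when it becomes permanent.

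A second reply is that both instructions can be met, since testing two or three times weekly also satisfies a weekly rule, and Section 10.2.2.5 speaks of monitoring without naming tests. It is true that no site is forced to breach one section in order to follow the other. But nothing in Section 10.2.2.3 or 10.2.2.5 tells the site that both apply, and Section 10.2.2.5 runs until laboratory findings settle, so it plainly includes the tests.

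A third reply is that other provisions limit the harm: extra safety samples (Section 10.2.1), extra clinic visits (Section 7.1.1), follow-up of unresolved events (Section 10.1.2) and review of liver values by the monitoring board (Section 11.2.4). These lower the risk. The extra samples and visits are discretionary, and none of these provisions fixes how often such a child is tested.

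Some of the objection stands. The group is narrow, its size and the duration of the state are unknown, and the document does not show how often such patients are still symptomatic and unstable when the stop becomes permanent. The file shown is one part of a larger document, so it cannot be confirmed here that this wording is the latest in force.

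**Conclusion.** The concern holds. For a patient permanently off drug for a liver or hepatitis reason, still symptomatic and with tests not stabilized, Section 10.2.2.2 calls for two or three liver tests a week and Section 10.2.2.5 for one. This is true under either reading of the step-down sentence. There is no conflict for asymptomatic patients, nor, on the ordinary reading, for those whose tests have stabilized.

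The size is a two- to threefold difference in testing frequency while that state lasts. Totals over time rest on assumed durations, and the number of patients is not given. The point is a safety-monitoring inconsistency that should be corrected. It does not bear on the efficacy analysis. Confidence is medium, because a careful investigator may already read weekly as a minimum.

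**What to change.** Change Section 10.2.2.5 at the next amendment, after confirming that the wording is still in force. Suggested content:

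> Patients permanently off study drug for a safety reason are monitored at least weekly until their laboratory and clinical findings are normal or stable. Where the reason is liver findings or hepatitis, liver enzymes and bilirubin remain on the Section 10.2.2.2 schedule of two or three tests a week until the abnormalities stabilize or the patient is asymptomatic.

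This leaves weekly monitoring as the minimum for diarrhea and other events and reuses the step-down conditions the protocol already has. Adding only the words *at least* would help, but would still not tell sites that the close-observation schedule continues.

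The cost is one amended provision and one or two extra blood draws a week, in what is likely to be a small number of children and only while they are both symptomatic and unstable. Section 10.2.2.2 already asks for those draws.
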